The primary objective will be analyzed using the time-to-first event Kaplan-Meier survival analysis method. Time 0 will be the day a subject undergoes the implant procedure of a Attain Stability Quad MRI SureScan LV Lead (Model 4798), which will be independent of success status of this implant procedure. Event date is the onset date of a subject's first complication that is related to the Attain Stability Quad MRI SureScan LV Lead (Model 4798) according to CEC adjudication. Subjects who undergo an Attain Stability Quad MRI SureScan LV Lead (Model 4798) implant attempt and do not experience any LV lead related complications will be censored at the time of their last known exposure to the Attain Stability Quad MRI SureScan LV Lead (Model 4798) for the survival analysis. For any lost-to-follow up subject, the last contact date will be used as the censor date. The 1-sided 97.5% confidence limit lower bound for the survival probability at 6 months (183 days) will be calculated using the log-log survival function approach (Kalbfleisch and Prentice 2002).

Sample Size Consideration

The primary safety objective performance criterion is set to be identical to Medtronic's Attain Performa Clinical Study (IDE Number: G120213). Therefore, the sample size calculation assumptions are derived based on the Model 4298 lead study results. The Attain Performa Model 4298 lead reported a 6-month complication free survival probably of 96.0%, with 97.5% Confidence Lower Limit of 94.3% (PMA-s clinical report).

The binomial calculation (Z-test) is used for initial sample size estimation. In order to preserve the overall study power, a type II error less than 10% was used for the sample size calculation. A sample size of 170 subjects completing their 6-month visit achieves greater than 90% power to detect a difference of 7% using the one-sided binomial test. The target significance level is 0.025. These results assume that the population proportion under the null hypothesis is 87% with an expected value of 94% (Figure 5). To account for 15% attrition, the enrollment size for this objective is 200.

Figure 5: Primary Safety Objective Sample Size Consideration by Difference Performance Assumption**Determination of Patients / Data for Analysis**

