19.1.2. Primary Efficacy Objective #1**Objective**

The Attain Stability Quad MRI SureScan LV Lead (Model 4798) will meet the first primary efficacy objective if the proportion of subjects with at least one Attain Stability Quad MRI SureScan LV Lead (Model 4798) pacing vector having a pacing capture threshold (PCT) less than or equal to 2.5 V at 0.5ms pulse width at 6 months post-implant is greater than 80% (i.e., the lower bound of the one-sided 97.5% confidence interval must be greater than 80%).

Hypothesis

$H_0: P_{1_{6\text{-month}}} \leq 80\%$

$H_A: P_{1_{6\text{-month}}} > 80\%$,

[figure not shown]
where $P_{1_{6\text{-month}}}$ is the proportion of subjects with pacing voltage thresholds $\leq 2.5\text{V}$ at 0.5ms at 6 months follow-up visit post-implant for at least one LV lead pacing vector.

Endpoint Justification

The Attain Stability Quad MRI SureScan LV Lead (Model 4798) is equipped with the identical four electrodes to the Attain Performa LV leads. At the same time, the unique fixation mechanism may cause the distal end of the lead (tip) to be implanted away from the apical region of the heart, and therefore

the PCT may be slightly higher than the values observed in other Quadripolar LV leads. Therefore, we simulated the lead pacing threshold values based on the Attain Performa IDE study data, but excluding the PCT values collected at the most distal electrode. The simulation estimated that 89% of the subjects will achieve this endpoint (Figure 6).

Figure 6: Simulated PCT Distribution

Statistical Analysis Methods

All subjects with valid pacing thresholds measured at the 6 month follow-up visit will be included in this analysis. The proportion of subjects having at least one LV lead pacing vector with voltage thresholds less than or equal to 2.5V will be calculated. The lower bound of the 1-sided 97.5% Confidence Interval will be calculated using the Exact binomial method. Any subject in which no valid pacing threshold value is measured or who has an unable-to-capture result via all LV lead pacing vectors will be reviewed and adjudicated for a possible lead related AE but will not be included for this evaluation if the occurrence is deemed to be a system related event (e.g. lead dislodgement). However, this event may be counted against the safety primary endpoint based on the CEC's final classification.

Sample Size

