The primary efficacy endpoint will be analyzed using the Exact binomial method. In order to preserve the overall study power, a type II error less than 10% was used for the sample size calculation. A sample size of 145 subjects achieves 91% power to detect a difference of 0.1 using a one-sided binomial test at a target significance level of 0.025. These results assume that the population proportion under the null hypothesis is 80%, with an expected proportion of 90%.

Determination of Patients / Data for Analysis

All subjects enrolled into this study satisfying the following conditions will be included in this analysis:

- Successfully implanted with a Medtronic Quad CRT-P or CRT-D device and Attain Stability Quad MRI SureScan LV Lead (Model 4798)
- Completed 6-month follow-up visit
- Initially implanted Attain Stability Quad MRI SureScan LV Lead (Model 4798) is active at the 6-month follow-up visit
- At least one available and valid pacing threshold at the 6-month follow-up visit

19.1.3. Primary Efficacy Objective # 2

Objective

The Attain Stability Quad lead will meet the second primary efficacy objective if the proportion of subjects with at least one additional (or second) LV lead pacing vector having a pacing capture threshold less than or equal to 4.0 V at 0.5ms pulse width at 6 months post-implant is greater than 80% (i.e., the one-sided 97.5% lower confidence bound must be greater than 80%).

Hypothesis

$$H_0: P_{2_{6\text{-month}}} \leq 80\%$$

$$H_A: P_{2_{6\text{-month}}} > 80\%$$

where $P_{2_{6\text{-month}}}$ is the proportion of subjects with at least one additional LV lead pacing vector with pacing voltage thresholds $\leq 4.0V$ at 0.5ms at 6 months post-implant follow-up visit.

Endpoint Justification

The Attain Stability Quad MRI SureScan LV Lead (Model 4798) has 16 LV programmable pacing vectors . Subjects may have the pacing configuration programmed or reprogrammed at each clinic visit. A pacing threshold of 4.0 V will allow an adequate safety margin for programming LV pacing output. The maximum pacing amplitude of the CRT-P or CRT-D devices capable of programming pacing output to any LV lead pacing vector is 8.0V. In actual clinical practice, a less than 3V safety margin is used for the programmed LV lead pacing output in 99% of the patients.

Statistical Analysis Methods

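### The primary safety objective's 170 completers give about 86% power under the planned analysis, not more than 90%; the trial's overall size makes this a correction of text only

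*Protocol*

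**What the plan says.** Section 19.1.1 (Sample Size Consideration) describes the safety calculation as follows.

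- Method: "The binomial calculation (Z-test) is used for initial sample size estimation".
- Target: "a type II error less than 10% was used for the sample size calculation".
- Result: "A sample size of 170 subjects completing their 6-month visit achieves greater than 90% power to detect a difference of 7" percentage points, "using the one-sided binomial test. The target significance level is 0.025".
- Assumptions: "These results assume that the population proportion under the null hypothesis is 87% with an expected value of 94" percent.

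The analysis itself is Kaplan-Meier. The one-sided 97.5% lower limit at 183 days "will be calculated using the log-log survival function approach", and success requires that limit to exceed 87%.

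For efficacy #1, the Endpoint Justification in 19.1.2 reports a simulation from earlier lead data with the most distal electrode left out: "The simulation estimated that 89% of the subjects will achieve this endpoint (Figure 6"). The Sample Size paragraph then claims 91% power for 145 subjects against a null of 80%, "with an expected proportion of 90" percent.

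Table 18 lists 170 completers (200 enrolled) for safety and 145 (171 enrolled) for efficacy #1. The overall requirement is 400 completers (471 enrolled), which comes from secondary objective #2.

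**The concern.** The safety statement gives a null rate, an alternative, a sample size, a significance level and a power, so it can be checked directly. The check falls short of 90% for the test that the protocol will use. If the row stood alone, the chance of missing the objective at a true rate of 94% would be about one in seven, where the section says less than one in ten.

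The efficacy #1 row raises a different question. Its arithmetic is right, but it uses a success rate one point better than the section's own simulation and does not say why.

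**Working it through.** **Inputs for safety (19.1.1).** n = 170, p0 = 0.87, p1 = 0.94, one-sided α = 0.025. X is the number of subjects free of a lead-related complication.

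**Step 1: reproduce the printed figure.** An estimated-variance (Wald) rule passes when p̂ − 1.96·√(p̂(1−p̂)/170) > 0.87.

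- X = 155: p̂ = 0.9118, limit 0.8691, fail.
- X = 156: p̂ = 0.9176, limit 0.8763, pass.

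The rule is therefore X ≥ 156. P(X ≥ 156 | 0.94) = 0.912, which matches a claim of more than 90%. But P(X ≥ 156 | 0.87) = 0.0357, above the 0.025 target. The plain normal formula for the same test, Φ(0.07·√170/√(0.94·0.06) − 1.96), gives 97.0%.

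**Step 2: rules that keep 0.025.**

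- *Exact binomial.* X ≥ 156 has error 0.0357 and X ≥ 157 has 0.0196, so the cutoff is 157. Power is P(X ≥ 157 | 0.94) = 0.856.
- *Null-variance Z-test.* z = (p̂ − 0.87)/√(0.87·0.13/170) is 1.85 at 156 and 2.08 at 157. The cutoff is again 157 and the power 0.856. By formula, Φ((0.07·√170 − 1.96·√(0.87·0.13))/√(0.94·0.06)) = Φ((0.9127 − 0.6592)/0.2375) = Φ(1.07) = 0.857.
- *Planned log-log bound, no censoring assumed.* The limit is S^exp(1.96·√v), with v = (1−S)/(170·S·(ln S)²). At 156 it is 0.8649 (fail) and at 157 it is 0.8719 (pass). The cutoff is 157 and the power 0.856.

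All three give a type II error of 1 − 0.856 = 14.4%.

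**Step 3: size needed for 90% (exact test, 87% against 94%).** Power first reaches 90% at n = 186 (0.905). It falls below at 188–194 and again at 202–204, and stays at or above 90% from n = 205 (0.931). The saw-tooth arises because the cutoff is a whole number. The null-variance Z formula gives 190.

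**Step 4: efficacy #1 (19.1.2).** n = 145, p0 = 0.80, exact test, cutoff X ≥ 126 (error 0.0204).

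- At 90%: power 0.913, so the stated 91% reproduces.
- At the simulated 89%: power 0.828.
- For 90% power at 89%: first reached at 173, sustained from 185.

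**Step 5: power at the trial's actual size (exact test).** Section 19.2.2 allows enrolment of 363 to 400. The second row below is an assumption: 363 enrolled less 15% attrition, 363 × 0.85 = 308.

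| Completers | Safety at 94% | Efficacy #1 at 89% |
|---|---|---|
| 400 (Table 18 overall) | 99.8% | 99.9% |
| 308 (assumed) | 98.8% | 99.1% |

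**Attrition.** 170/0.85 = 200, 145/0.85 = 171 and 400/0.85 = 471 are all correct.

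**The case against.** The protocol names a Z-test for initial sizing, does not state its variance form, and calls 0.025 a target level. With the estimated variance, more than 90% reproduces, so this need not be a slip in arithmetic. That stands as the likely origin of the figure. It does not make the sentence true of the plan: with exactly 156 of 170 event-free, the Wald rule passes and the planned log-log bound fails. Figure 5, which the protocol cites for these assumptions, is not shown, so the sponsor's curve could not be checked.

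Planning at 94% is also cautious. The protocol expects performance like Model 4298, at 96.0%, where 170 completers would give 99.1% by the exact test. That is fair, but the printed power is tied to 94%.

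Two stronger readings are tempting, and the document supports neither.

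- A reader might infer that the efficacy #1 row is wrong too. It is not: it delivers the stated 91% at the stated 90%. The 89% shows only a more favourable assumption left unexplained.
- A reader might infer that the per-objective rows are a fallback should enrolment stop short. No section gives them that role. Section 19 ties the analysis to meeting the Table 18 requirements for all objectives.

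**Conclusion.** The safety power statement does not hold for the planned analysis: 85.6% rather than more than 90%, with a type II error of 14.4% rather than below 10%. This assumes independent binomial outcomes and, for the log-log bound, no censoring before 183 days. The printed figure is best described as reproducible only with a test that exceeds the stated significance level.

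The efficacy #1 power is correct as stated. At the section's own simulated rate it would be about 83%, and the choice of 90% needs a reason.

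The practical effect is small. At 400 completers both objectives have power above 99%, and at an assumed 308 they have about 99%. This is a misstated property of one row, and no conclusion of the trial is at risk.

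**What to change.** Change the text of 19.1.1 and 19.1.2, and Table 18 where needed.

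1. In 19.1.1, restate safety power as about 86% at 170 completers under the planned analysis and remove the claim of a type II error below 10%. Alternatively, list about 205 completers as the number needed (205/0.85 = 241.2, so 242 enrolled for that row) and note the saw-tooth between 186 and 205.
2. State power at the size the trial will have: 99.8% for safety at 400 completers. If a lower figure is wanted, give 98.8% at about 308 and state the assumption of 363 enrolled less 15%. The 363 to 400 range in 19.2.2 is worded as enrolled patients and should not be relabelled as completers.
3. In 19.1.2, keep 91% at 90% and add that at the simulated 89% power is about 83% with 145 subjects and 99.9% with 400, or explain why 90% was used.

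The cost is a few sentences and possibly one table row. Enrolment and the analysis do not change.

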19.1.2. Primary Efficacy Objective #1**Objective**

The Attain Stability Quad MRI SureScan LV Lead (Model 4798) will meet the first primary efficacy objective if the proportion of subjects with at least one Attain Stability Quad MRI SureScan LV Lead (Model 4798) pacing vector having a pacing capture threshold (PCT) less than or equal to 2.5 V at 0.5ms pulse width at 6 months post-implant is greater than 80% (i.e., the lower bound of the one-sided 97.5% confidence interval must be greater than 80%).

Hypothesis

$H_0: P_{1_{6\text{-month}}} \leq 80\%$

$H_A: P_{1_{6\text{-month}}} > 80\%$,

[figure not shown]
where $P_{1_{6\text{-month}}}$ is the proportion of subjects with pacing voltage thresholds $\leq 2.5\text{V}$ at 0.5ms at 6 months follow-up visit post-implant for at least one LV lead pacing vector.

Endpoint Justification

The Attain Stability Quad MRI SureScan LV Lead (Model 4798) is equipped with the identical four electrodes to the Attain Performa LV leads. At the same time, the unique fixation mechanism may cause the distal end of the lead (tip) to be implanted away from the apical region of the heart, and therefore

the PCT may be slightly higher than the values observed in other Quadripolar LV leads. Therefore, we simulated the lead pacing threshold values based on the Attain Performa IDE study data, but excluding the PCT values collected at the most distal electrode. The simulation estimated that 89% of the subjects will achieve this endpoint (Figure 6).

Figure 6: Simulated PCT Distribution

Statistical Analysis Methods

All subjects with valid pacing thresholds measured at the 6 month follow-up visit will be included in this analysis. The proportion of subjects having at least one LV lead pacing vector with voltage thresholds less than or equal to 2.5V will be calculated. The lower bound of the 1-sided 97.5% Confidence Interval will be calculated using the Exact binomial method. Any subject in which no valid pacing threshold value is measured or who has an unable-to-capture result via all LV lead pacing vectors will be reviewed and adjudicated for a possible lead related AE but will not be included for this evaluation if the occurrence is deemed to be a system related event (e.g. lead dislodgement). However, this event may be counted against the safety primary endpoint based on the CEC's final classification.

Sample Size

The primary efficacy endpoint will be analyzed using the Exact binomial method. In order to preserve the overall study power, a type II error less than 10% was used for the sample size calculation. A sample size of 145 subjects achieves 91% power to detect a difference of 0.1 using a one-sided binomial test at a target significance level of 0.025. These results assume that the population proportion under the null hypothesis is 80%, with an expected proportion of 90%.

Determination of Patients / Data for Analysis

All subjects enrolled into this study satisfying the following conditions will be included in this analysis:

- Successfully implanted with a Medtronic Quad CRT-P or CRT-D device and Attain Stability Quad MRI SureScan LV Lead (Model 4798)
- Completed 6-month follow-up visit
- Initially implanted Attain Stability Quad MRI SureScan LV Lead (Model 4798) is active at the 6-month follow-up visit
- At least one available and valid pacing threshold at the 6-month follow-up visit

19.1.3. Primary Efficacy Objective # 2

Objective

The Attain Stability Quad lead will meet the second primary efficacy objective if the proportion of subjects with at least one additional (or second) LV lead pacing vector having a pacing capture threshold less than or equal to 4.0 V at 0.5ms pulse width at 6 months post-implant is greater than 80% (i.e., the one-sided 97.5% lower confidence bound must be greater than 80%).

Hypothesis

$$H_0: P_{2_{6\text{-month}}} \leq 80\%$$

$$H_A: P_{2_{6\text{-month}}} > 80\%$$

where $P_{2_{6\text{-month}}}$ is the proportion of subjects with at least one additional LV lead pacing vector with pacing voltage thresholds $\leq 4.0V$ at 0.5ms at 6 months post-implant follow-up visit.

Endpoint Justification

The Attain Stability Quad MRI SureScan LV Lead (Model 4798) has 16 LV programmable pacing vectors . Subjects may have the pacing configuration programmed or reprogrammed at each clinic visit. A pacing threshold of 4.0 V will allow an adequate safety margin for programming LV pacing output. The maximum pacing amplitude of the CRT-P or CRT-D devices capable of programming pacing output to any LV lead pacing vector is 8.0V. In actual clinical practice, a less than 3V safety margin is used for the programmed LV lead pacing output in 99% of the patients.

Statistical Analysis Methods

The efficacy endpoint #2 will be analyzed using the Exact binomial method. The proportion of subjects with at least 2 LV lead pacing vectors having voltage thresholds less than or equal to 4.0V at 0.5ms will be calculated. The lower bound of the 1-sided 97.5% Confidence Interval will be calculated using the Exact binomial method. Any subject in which no valid pacing threshold values are measured or with an Unable-to-capture result via all LV lead pacing vectors will be reviewed and adjudicated for possible lead related complications, and therefore may be counted against the study safety endpoint. However, it will be counted as a failure if there is not any additional LV lead pacing vectors (excluding the vector that is already include for the efficacy endpoint #1) are unable to capture with no lead related events reported.

Sample Size

The Attain Performa Model 4298 LV lead observed 97.7% subjects who were able to obtain a non-programmed pacing vector with PCT less than or equal to 4 volts. A sample size of 50 subjects completing the 6 month visit achieves 98% power to detect a difference of 0.18 using a one-sided binomial test at a target significance level of 0.025. These results assume that the population proportion under the null hypothesis is 80%, with the expected proportion of 97%.

Determination of Patients / Data for Analysis

All subjects enrolled into this study satisfying the following conditions will be included in this analysis:

- Successfully implanted with a Medtronic Quad CRT-P or CRT-D device and Attain Stability Quad MRI SureScan LV Lead (Model 4798)
- Completed 6-month follow-up visit
- Initially implanted Attain Stability Quad MRI SureScan LV Lead (Model 4798) lead is active at the 6-month follow-up visit
- At least one available and valid pacing threshold at the 6-month follow-up visit. In the event a subject failed to provide more than one valid pacing threshold value, that subject will be considered as not having at least one additional LV lead pacing with PCT \leq 4.0V at 0.5ms at 6 months post-implant follow-up visit

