19.3.2. Sensitivity Analysis

All subjects enrolled into this study and successfully implanted with a Medtronic Quad CRT-P or CRT-D device and Attain Stability Quad MRI SureScan LV Lead (Model 4798) will be included in the primary efficacy analysis datasets (efficacy objectives #1 and #2). Sensitivity analysis such as the Tipping Point method or similar will be conducted to investigate the influence of subjects who were successfully implanted with the required system however missed a 6 month post implant follow-up test(s) (due to reasons such as missing in-office visit, subject exit, death and/or the initial implanted lead was deactivated). For this purpose, all subjects with successful implant who do not meet analysis cohort requirements, will be considered as the worst case scenario (i.e. failure to meet the efficacy endpoints). The results will be submitted as part of the clinical reports.

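### Both primary efficacy proportions leave out leads that failed for system-related reasons, so they describe working leads only and are biased upward

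*Protocol*

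**What the plan says.** The protocol file holds two versions; the rules below read the same in both.

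- **Hypotheses (19.1.2, 19.1.3).** P1 and P2 are proportions of subjects, with no restriction to leads that still work. Section 11.1.1 gives the aim as at least two programmable vectors for each patient after implant.
- **Objective #1, analysis methods (19.1.2).** A subject with no valid threshold or no capture on any vector is reviewed, but "will not be included for this evaluation if the occurrence is deemed to be a system related event (e.g. lead dislodgement"). The event may instead count against safety, depending on adjudication.
- **Objective #1, cohort (19.1.2).** The initial lead must be active at 6 months, with "At least one available and valid pacing threshold at the 6-month follow-up visit".
- **Objective #2 (19.1.3).** The cohort conditions are repeated. A garbled sentence counts a failure where additional vectors "are unable to capture with no lead related events reported". The last cohort bullet counts a subject with only one valid threshold as not meeting the objective.
- **System modifications (15.14).** A capped or explanted lead needs no further electrical testing. A second study lead implanted after a lead-related complication is left out of the objective analyses, apart from adverse events.
- **Sensitivity analysis (19.3.2).** Its first sentence says that all successfully implanted subjects "will be included in the primary efficacy analysis datasets (efficacy objectives #1 and #2"). It then plans a tipping-point or similar analysis that treats implanted subjects outside the cohort as failures.

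**The concern.** A lead that captures on no vector at 6 months, or that has been lost because of a lead problem, is the plainest failure to provide a usable pacing vector. Removing such subjects selects on the outcome, so the tested proportion is conditional on the lead still working. A lead that serves only 80% of its recipients could then be declared effective more often than the stated error rate allows.

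The denominator also cannot be settled from the text. The methods paragraph of 19.1.2 drops no-capture subjects only when the event is system related, which implies that the others stay in as failures. The cohort list appears to drop anyone without a valid threshold. The opening of 19.3.2 keeps everyone who was successfully implanted. These three readings give different denominators.

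**Working it through.** **Inputs.** Null 80%, expected 90%, one-sided 0.025, exact binomial bound (19.1.2); simulated success 89% (19.1.2); 400 subjects at 6 months, 471 enrolled (19.3.3, Table 18); safety goal 87% with a log-log bound (19.1.1). The share d of subjects excluded as lead failures is not given. I assume 1% to 5%. The only related figure is Model 4298's 96.0% complication-free rate at 6 months, i.e. 4% with complications (19.1.1). That probably overstates d, because some complications are repaired or are not capture failures.

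**The plan's own figure.** It states: "A sample size of 145 subjects achieves 91% power to detect a difference of 0.1". The objective passes if the exact lower bound, the 0.025 quantile of Beta(k, n − k + 1), exceeds 0.80. At n = 145 the pass mark is 126 (86.9%, bound 80.3%), exact type I error is 2.0%, and power at 90% is 91.3%. The stated 91% reproduces, so the sample-size arithmetic is sound; the issue is the analysis set.

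**Pass mark at n = 400.** 336/400 = 84.0%, bound 80.03%, exact type I error 2.4%.

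**Effect of the exclusion at a true 80%.** If a share d fails and is removed, success among those kept is 0.80/(1 − d). The chance of passing is P(X ≥ 336), with X binomial(400, 0.80/(1 − d)).

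| d | Success among those kept | Upward shift (points) | Chance of passing |
|---|---|---|---|
| 0 | 80.0% | 0 | 2.4% |
| 1% | 80.8% | 0.8 | 5.7% |
| 2% | 81.6% | 1.6 | 12.2% |
| 3% | 82.5% | 2.5 | 23.3% |
| 4% | 83.3% | 3.3 | 39.1% |
| 5% | 84.2% | 4.2 | 57.9% |

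If n also shrinks by d, the values for d = 1% to 4% become 5.3%, 10.6%, 19.4% and 37.1%.

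**A borderline result.** 336/400 passes. Restoring 4 excluded failures gives 336/404 = 83.2%, bound 79.2%, which fails.

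**The expected result.** 0.89 × 400 = 356. Adding back 24 failures gives 356/424, bound 80.1% (pass). Adding back 25 gives 356/425 = 83.8%, bound 79.9% (fail). So 25/425 = 5.9% would have to be excluded failures before the conclusion turned.

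**What the safety goal absorbs.** With 400 subjects and no censoring, S = 1 − e/400 and the bound is S^exp(1.96·se/(S·|ln S|)), where se = √(S(1 − S)/400). It is 87.18% for e = 38 and 86.90% for e = 39. Up to 38 subjects with complications (9.5%) still pass.

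**What the worst-case analysis demands.** As an upper bound, suppose all 471 − 400 = 71 lost subjects had been implanted and were scored as failures. The pass mark would be 395/471, or 395/400 = 98.75% of those evaluable.

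**The case against.** The protocol arguably assigns lead failure to safety and threshold performance to efficacy. The safety cohort is every implant attempt. A system- or procedure-related event that ends significant device function or needs invasive intervention is a complication, and the events committee adjudicates it. Section 19.3.2 already plans to score excluded implanted subjects as failures, names deactivated leads among them, and commits to reporting the result. Type I inflation is measured at exactly 80%, while the plan expects 89% to 90%.

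Much of this stands. The exclusion is disclosed, a worst-case count is planned, and the expected result is robust. It does not restore error control at the 80% boundary, however. The safety goal is a separate 87% criterion that can absorb several percent of lead failures. The worst-case analysis has no success criterion and mixes lead failures with missed visits, exits and deaths, so failing it would say little about the lead.

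Two stronger readings are tempting. A reader might infer that objective #2 scores a failure only when no lead-related event is reported. The last cohort bullet of 19.1.3 contradicts that, since a subject with only one valid threshold fails regardless of event reporting. A reader might also infer that every lead failure disappears. The methods paragraph of 19.1.2 implies that no-capture subjects without a system-related event stay in, and an initial lead that was repositioned and is active at 6 months is still counted.

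**Conclusion.** The point holds as a should-fix. Lead-caused failures leave the denominator of both primary efficacy objectives, the bias runs only upward, and the sections that define the denominator conflict. For objective #1 at n = 400 and a true 80%, the chance of passing is about 6% to 58% for d = 1% to 5%, against a nominal 2.5%, with an upward shift of 0.8 to 4.2 points. These sizes rest on the assumed d and on a true rate at the boundary. The documents do not support the inference that the study is likely to reach the wrong conclusion: if success is near the expected 89%, pass or fail would probably not change. What would change is the reported proportion and what it can be said to describe.

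**What to change.** In 19.1.2 and 19.1.3, count as failures for both objectives those successfully implanted subjects who, by the 6-month visit, have no capture on any vector, or whose initial lead was deactivated, capped, explanted or replaced for a lead-related reason. Leave only lead-unrelated missing data (deaths, exits, missed visits, removals for other reasons) to the 19.3.2 analysis. Report the present rule as a sensitivity analysis. Align the methods paragraphs, the cohort lists and the first sentence of 19.3.2, and rewrite the garbled failure sentence in 19.1.3.

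This needs wording only and no new data. The cost is a less favourable figure. With 89% success among evaluable subjects, the true rate becomes 0.89(1 − d) on n = 400/(1 − d):

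| d | n | True rate | Pass mark | Power, objective #1 |
|---|---|---|---|---|
| 1% | 404 | 88.1% | 340 | 99% |
| 2% | 408 | 87.2% | 343 | 97% |
| 3% | 412 | 86.3% | 346 | 93% |
| 4% | 417 | 85.4% | 350 | 83% |
| 5% | 421 | 84.6% | 354 | 63% |
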